## 1. ABBREVIATION AND DEFINITION LIST

AE	Adverse Event
Ave.	Avenue
cm	Centimeter
GCP	Good Clinical Practices.
ICF	Informed Consent Form
ICH	International Conference on Harmonisation
PDF	Portable Document Format
SAE	Serious Adverse Event
SOP	Standard Operating Procedure
Test Article/Product	These terms may appear interchangeably in the protocol and are defined as the test article/product used in the study
Subject/Participant	These terms may appear interchangeably in the protocol and are defined as the individual(s) that will participate in the study.

## 2. OBJECTIVE

To determine the sensitization (contact allergy) potential of test product ColActive Plus Collagen Matrix Dressing after a skin prick test to the skin of human subjects.

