## 7. EXPERIMENTAL TECHNIQUES AND METHODS

This will be a single center, with no randomization or blinding, study design in 30 healthy adult subjects, age 18-70 years. Based on prior experience approximately 30 subjects will be enrolled to ensure 20 subjects complete the study.

Skin response to the test product and both positive and negative controls will be evaluated and measured by an allergist. If the measured diameter is  $\geq 3$ mm in response to the test product with expected reactions to both the positive and negative controls, the site will be considered a positive allergen.

Initial reading will take place after 15 minutes looking for the presence or absence of a wheal and flare at all three sites and measuring the diameter of both the wheal and flare if present. The wheal at the positive control must exceed a wheal at the negative control by 3 mm. A second reading is conducted about 6 hours after the SPT administration and similar measurements are taken. The subjects return to the office 1-2 days after the initial administration for a third test reading and measurements. A positive reaction is present when there is a measurable wheal of  $>3$  mm. Small wheals are confirmed by palpation. The skin prick reaction is quantified by measuring the mean diameter of the wheal, using a ruler marked in mm. If the result is a circular wheal, one measurement of the diameter (in mm) is sufficient; if ovoid or irregular, two diameters are measured (smallest and largest) and the numbers are added and divided by 2 (mean diameter). A flare alone is measured but is not of any clinical significance. The flare, area of erythema, may also be recorded by the same method.

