## 8. BACKGROUND

Skin prick testing (SPT) is a standard method for diagnosing allergic sensitization. SPT interpretation utilizes the presence and degree of cutaneous reactivity as a surrogate marker for sensitization within target organs, i.e., eyes, nose, lung, gut, and skin. When relevant allergens are introduced into the skin, specific IgE bound to the surface receptors on mast cells are cross-linked, mast cells degranulate, and histamine and other mediators are released. This produces a wheal and flare response which can be quantitated. Many different allergens can be tested simultaneously because the resultant reaction to a specific allergen is localized to the immediate area of the SPT.

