## 9. PROCEDURE

### 9.1 Consent

Subjects will be given an informed consent form (ICF), inclusive of a HIPAA disclosure and California Subject Bill of Rights, to read and sign. They will have all of their study related questions answered by the Investigator or designated staff. Subjects who qualify based on the inclusion and exclusion criteria will be enrolled into the study.

*9.2 Method of Application:*

UniTest PC device through a drop of allergen extract. All applications will be to the volar forearm.

*9.3 Test Product/Equipment:*

The test product will be provided by the sponsor. Test product will be applied using a UniTest PC device to the test site (volar forearm). Aliquot all test articles into their respective sterile reservoir to serve as a basin during application.

*9.4 Test Product Preparation / Application:*

Test Product Preparation will be performed as noted below unless otherwise requested by Sponsor.

*Step 1: ColActive Plus Collagen Matrix Dressing: cut with sterile scissors into a 25-millimeter diameter.*

*Step 2: 0.8mL of distilled water will be dispensed to saturate the test product.\**

*Step 3: Aliquot test product into a reservoir to allow for the UniTest PC device to be dipped into the test product.*

*Step 4: Use the UniTest PC device to apply the test product to the subject volar forearm skin.*

*\*Visual inspection will be done to confirm saturation of the dressing with distilled water and test product has transformed into a gel.*

*9.5 Test Sites:*

The test product ColActive Plus Collagen Matrix Dressing, Positive control and Negative control will be applied directly to the volar forearm skin of the subject. The sites will be a minimum of 2cm from each other to minimize cross contamination.

Positive Control:

Use the UniTest PC device and apply the histamine positive control to subjects volar forearm.

Negative Control:

Use the UniTest PC device and apply the saline with glycerin (bacteriostatic) negative control, to subjects volar forearm.

Test sites should be more than 5 cm from the wrist and 3 cm from the antecubital fossa and marked by numbers on the skin to identify the test article, negative control and positive control.

*9.6 Procedure:*

The test area will be cleaned with an alcohol pad. A series of marks will be made using a skin pen on the subjects' volar forearm.

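### The objective claims sensitization (contact allergy) potential, but one prick judged by wheal can describe only wheal reactivity to that prick

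*Combined protocol and SAP*

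**What the plan says.** Section 2 states the only objective: "To determine the sensitization (contact allergy) potential of test product ColActive Plus Collagen Matrix Dressing after a skin prick test". The term contact allergy is not among the entries of Section 1 ("ABBREVIATION AND DEFINITION LIST") and does not recur in the text available.

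Section 8 explains the method. It says "Skin prick testing (SPT) is a standard method for diagnosing allergic sensitization" and gives the mechanism: "specific IgE bound to the surface receptors on mast cells are cross-linked, mast cells degranulate, and histamine and other mediators are released". It also treats skin reactivity as a "surrogate marker for sensitization within target organs, i.e., eyes, nose, lung, gut, and skin".

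Section 9.5 sets out the sites: the dressing, with the histamine and saline-glycerin controls, for which "Positive control and Negative control will be applied directly to the volar forearm skin of the subject". Section 9.6 describes dipping the device in the prepared product and pricking the forearm. Sections 7, 9.6 and 14 give three readings after that prick, at about 15 minutes, 6 hours and 24-48 hours.

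Positivity is defined by wheal size. Section 7 places a wheal rule directly after the last reading ("for a third test reading and measurements. A positive reaction is present when there is a measurable wheal of", followed by the 3 mm threshold) and adds: "A flare alone is measured but is not of any clinical significance". Section 14 then bases reporting for skin sensitization on positive scores at each interval.

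**The concern.** The objective names a property of the product: its potential to sensitize, glossed as contact allergy. The procedure observes a response in the subject: whether a wheal forms at a prick site. These are different quantities, and the plan does not say how the second answers the first.

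The word *potential* can be read in two ways. It may mean capacity to induce sensitization in people who do not have it, or capacity to elicit a reaction in people who do. The objective does not choose. The first reading is beyond the design. The second is nearer to what Section 8 describes, but the objective would have to say so.

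What is at stake is the study's only conclusion. Section 4 describes a topically applied wound dressing, so a reader will want to know about contact use. If every product site is negative, the report could follow the plan exactly and still be taken as evidence of no contact-allergy potential, which the data would not show.

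**Working it through.** No figure in the plan sizes this point. The one calculation, n = 20 at 99% confidence with an interval of 1.35 (Section 14), concerns precision. It gives no standard deviation or unit, so it cannot be reproduced, and it has no bearing on what is being measured. The check is therefore a count of design elements and a comparison of sections.

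**Counts from the documents**
- Pricks per subject: product 1 + positive control 1 + negative control 1 = 3 (Section 9.5).
- Repeat applications of the product: 0. Later challenges: 0 (Sections 7, 9.4 to 9.6 and 14). Appendix I gives the study length as 3 days.
- Readings: 3, all after the same prick (Section 14).
- Findings that count as positive: 1, a wheal at the 3 mm threshold (Sections 7 and 9.6).
- Definition-list entries: AE, Ave., cm, GCP, ICF, ICH, PDF, SAE, SOP, Test Article/Product, Subject/Participant = 11. None defines contact allergy or sensitization.
- Occurrences of contact allergy in the text available: 1, in Section 2.

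**Claim against design**

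| What a claim would need | What the plan provides |
|---|---|
| Induction: an exposure, then a later test of whether reactivity to the product has arisen | One prick, which is both the exposure and the test; no second application |
| Contact allergy: a definition and a finding that would show it | No definition; the only positive finding is a wheal |
| Wheal reactivity to a prick: a prick, controls, a wheal measurement and a rule | All four are present |

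**Reasoning**
1. By the mechanism in Section 8, a wheal arises when the introduced allergen cross-links IgE bound to mast cells. The result concerns how the subject responds to this prick.
2. Suppose the dressing could induce sensitization in people not already sensitized. With no later test, the plan has no observation designed to reveal it.
3. Suppose the dressing could not. A table with no positives would be an expected result in that case too.
4. Because the planned observations do not separate cases 2 and 3, an all-negative table cannot support a statement about induction.
5. The same holds for contact allergy that appears without a wheal. Such a reaction might be recorded, but the plan would not score it positive.
6. None of these steps depends on the number of subjects. Completing 20 or 30 changes the precision of a wheal rate, not the property it estimates.

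**The case against.** The strongest reply is that the objective limits itself. It ties the claim to a skin prick test, Section 8 explains what that test detects, and skin is among the target organs listed there. Section 14 speaks of skin sensitization and does not repeat the contact-allergy gloss. Further, since the documents never define contact allergy, they cannot prove that it works by another mechanism.

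Part of this stands. Section 8 does support reading a wheal as a marker of allergic sensitization, and the documents do not establish that contact allergy is mechanistically different. The point here is narrower: the term has no definition and no finding attached to it, and one prick cannot show induction. Naming the procedure in the objective does not remove the words *contact allergy* and *potential* from the claim.

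Stronger readings are tempting, but the documents do not support them:
- **That the late readings have no positivity rule.** Section 7 gives a general wheal rule after describing all three readings, Section 9.6 has the wheal of each test measured and refers back to Section 7, and Section 14 calls for scores at each interval. A rule exists. That its threshold is written both as at least 3 mm and as more than 3 mm is a separate matter.
- **That reactions without a wheal would be lost.** Section 7 provides for measuring flare, Section 11 requires adverse events to be recorded, and Section 14 tabulates skin responses by subject. Such reactions can be captured; they are not counted as positive.
- **That every wheal, late ones included, can be labelled existing IgE-type sensitization.** Section 8 describes the mechanism in general and says nothing specific about readings at 6 or 24-48 hours.
- **That excluding known fish allergy is part of this fault.** Section 5.2 states the exclusion openly. How far the result generalizes is a separate question.

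**Conclusion.** The point holds as a mismatch between the stated claim and the method. A plan followed to the letter would report on a property, capacity to sensitize or contact allergy, that the design cannot show. It can support a description of wheal reactivity to a single prick in the enrolled healthy adults.

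The size is qualitative. One sole objective and one reporting phrase are affected, and no rate, bound or sample-size figure measures the effect. It should be fixed because it governs the only conclusion the study will draw.

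The conclusion rests on two assumptions: that *potential* may be read as capacity to induce, which the text leaves open, and that no further exposure or definition exists outside the text available. A reader might infer that the prick test itself is unsound or that an induction-and-challenge design is required. The documents do not support that. The procedure is adequate for the narrower statement, and the wording is what needs to change.

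**What to change.** Three wording changes, made by amendment under Section 12:

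1. **Section 2.** Replace the objective with: *To describe skin prick test wheal reactivity to ColActive Plus Collagen Matrix Dressing at 15 minutes, 6 hours and 24-48 hours in the enrolled healthy adults.* This removes the reference to sensitization (contact allergy) potential.
2. **Section 14, product reporting.** Replace the reference to skin sensitization with *skin prick test wheal reactivity*.
3. **Section 14, added sentence.** *The result does not address induction of sensitization or contact allergy without a wheal.*

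Procedures, readings, eligibility, sample size and the planned per-subject table are unchanged. The cost is the amendment itself (written approval by the client and the testing facility, then IRB approval) and a narrower claim for the sponsor.

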## 3. QUALITY REVIEW AND VERIFICATION

This study will be conducted in adherence to Good Clinical Practice Regulations (21 CFR 50: Protection of Human Subjects-Informed Consent). These procedures are designed to ensure adherence to the spirit of Good Clinical Practices (GCPs), as described in:

- International Council for Harmonization (ICH) of Technical Requirements for Pharmaceuticals for Human Use, ICH Harmonized Tripartite Guidelines for Good Clinical Practice 2023 [ICH E6 (R3)].
- US 21 CFR dealing with clinical studies (including part 50 concerning informed consent).
- Declaration of Helsinki, concerning medical research in humans (Recommendations Guiding Physicians in Biomedical Research Involving Human Subjects, Helsinki 1964, amended Tokyo 1975, Venice 1983, Hong Kong 1989, Somerset West 1996, Edinburgh 2000, Washington 2002, Tokyo 2004, Seoul 2008, and Brazil 2013).

[figure not shown]
The Investigator agrees when signing the protocol to adhere to the instructions and procedures described in it and, thereby, to adhere to the GCPs to which it conforms.

The study data and final report will be reviewed and signed by Quality Assurance staff.

The Investigator will permit trial related monitoring, audits and regulatory inspections and will provide copies of, and direct access to, source data/documents.

## 4. TEST PRODUCT

ColActive Plus Collagen Matrix Dressing is an advanced wound dressing made from fish-derived collagen, sodium alginate, carboxymethylcellulose (CMC), and ethylenediaminetetraacetic acid (EDTA). ColActive Plus is a topically applied wound dressing that will transform into a soft gel sheet when in contact with wound exudates.

An adequate amount of test article will be supplied by the Sponsor in containers suitable for use by the testing facility. Enough test products will be supplied to last for the maximum number of subjects for the entire study duration. Responsibility of the identity, purity, strength, safety, composition, and stability of the test articles will remain with the Sponsor. Additionally, by signing this protocol the Sponsor confirms that the test articles being evaluated are composed of common cosmetic ingredients with a known, favorable, safety profile and do not pose a known health risk when used as intended. The test articles will be stored in a secured location with the temperature monitored until use.

Upon arrival at ALS the test product will be assigned a unique laboratory code number and entered into a daily log identifying the lot number, sample description, sponsor, date received, and tests requested.

Sample will be retained for a minimum of 30 days beyond submission of final report. Sample disposition will be conducted in compliance with appropriate federal, state, and local ordinances.

## 5. SUBJECT SELECTION CRITERIA

Approximately 30 healthy subjects satisfying all criteria listed below will be enrolled to complete the study with a minimum of 20 subjects.

## 5.1 Inclusion Criteria

Individuals included in the study will be enrolled based upon the following criteria.

1. Age: 18-70
2. Sex: Male & Female
3. Fitzpatrick: I-V, minimum 10% of panel Fitzpatrick V.
4. Individuals who will be able to read, understand and give an informed consent relating to the study they are participating in.
5. Individuals who will be free of any dermatological or systemic disorder, which in the Investigator's opinion, could interfere with the study results.
6. Individuals who will be in general good health and who will complete a preliminary medical history form mandated by the testing facility.
7. Individuals who will be able to and agree to cooperate with the Investigator and clinical staff.
8. Individuals who will agree to have test products applied in accordance with the protocol and are able to complete the full course of the study.
9. Individuals who have not participated in a similar study in the past 30 days.
10. Individuals who agree to refrain from sun tanning/bathing and prolonged exposure to sunlight (outdoors).
11. Individuals who are willing to refrain from wetting, wiping, cleanse, and covering the test sites (volar surface of the forearms) between the baseline and up to 48-hour time points.
12. Female volunteers who are willing to undergo a urine pregnancy test.
13. Individuals willing to refrain from vitamin C (Emergen-C), orange juice and vitamin water for the study duration and two days prior to the SPT test.

## 5.2 Exclusion Criteria

Individuals meeting any of the following criteria will be excluded from study participation.

1. Individuals who are currently taking any medications (topical or systemic) that may mask or interfere with the test results (specifically, corticosteroids, topical and/or systemic [except nasal steroids], non steroidal anti-inflammatory drugs [e.g. ibuprofen, Advil, Motrin, aspirin > 325mg/day], antihistamines, and topical/oral immunosuppressive medications).
2. Individuals who have a history of any acute or chronic disease that might interfere with or increase the risk on study participation. (e.g., systemic lupus erythematosus, rheumatoid arthritis, HIV positive).
3. Individuals who are diagnosed with chronic skin allergies (atopic dermatitis/eczema) or recently treated skin cancer within the last 12 months.
4. Individuals who have damaged skin in close proximity to test sites (e.g., sunburn, uneven skin pigmentation, tattoos, scars, excessive hair, active acne papules or other disfigurements).
5. Individuals who control their diabetes using insulin.
6. Individuals with any history, which in the Investigator's opinion, indicates the potential for harm to the subject or places the validity of the study in jeopardy.
7. Female volunteers who indicate that they are pregnant or are planning to become pregnant or nursing.
8. Individuals with a known history of hypersensitivity to any cosmetics, personal care products, fragrances, and/or adhesives.
9. Individuals that have a history of dermatographism.
10. Individuals have a history of frequent skin irritation.
11. Employees of ALS.
12. Individuals with a known fish allergy.

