## **14. STATISTICAL RATIONALE AND DATA REPORTING**

Evaluation of results consists of only one physiological measure (that of wheal/flare) measured at 3 time points: T1=15 minutes after SPT, T2=6hr after SPT and T3=24-48 hrs. after SPT. Our power analysis calculation indicates at a confidence level of 99% and confidence interval of 1.35, we will need a sample size of n=20. No statistical analysis will be performed. No significant effect or interaction effects are anticipated hence the small sample size. Skin responses to the test product and controls for each subject will be presented in a table in the final report.

Product reporting for skin sensitization will be based on statistically significant positive scores at each interval. Any subject that has erythema present in the negative control eliciting an allergic response will be included as long as the wheal diameter of the positive control exceeds the wheal size of the negative control by at least 3mm. This is to account for individuals who have sensitive skin. This data will be noted in the clinical findings.

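### The sensitization conclusion is not limited to the population tested, which leaves out known fish allergy although the dressing is made from fish collagen

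*Combined protocol and SAP*

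**What the plan says.** Section 4 describes the product as an "advanced wound dressing made from fish-derived collagen", together with sodium alginate, CMC and EDTA. The collagen is the only component described as coming from an animal.

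Section 8 explains what a positive prick test reflects: "specific IgE bound to the surface receptors on mast cells are cross-linked", after which mast cells degranulate and a wheal forms. On that account the test reads sensitization that is already present. The plan has one prick session with readings at 15 minutes, 6 hours and 24-48 hours, and no earlier exposure to the product.

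Section 5.2 then sets the population:
- item 12 excludes "Individuals with a known fish allergy", and question 2 of the Appendix I recruitment questionnaire screens for it again;
- item 8 excludes "Individuals with a known history of hypersensitivity to any cosmetics, personal care products, fragrances, and/or adhesives";
- item 3 excludes diagnosed chronic skin allergy (atopic dermatitis or eczema).

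Sections 5 and 7 call the panel healthy subjects: about 30 enrolled so that at least 20 complete.

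The aim in Section 2 is the sensitization potential of the product "after a skin prick test to the skin of human subjects". Section 14 states: "Product reporting for skin sensitization will be based on statistically significant positive scores at each interval". Neither sentence limits the conclusion to the people who pass Section 5.2.

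**The concern.** The test reads existing IgE, and the product's animal-derived component is fish collagen. People already known to be allergic to fish are a group in which a reader would want to know the response, and none of them is to be tested. Leaving them out may well be right for safety, and this point does not question it. The difficulty is that the result is then framed as a property of the product.

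If the table comes back all negative, nothing in the plan makes the report say that known fish-allergic users were left out by design. The result could then be read as reassurance for people about whom the study has no data. A larger panel with the same exclusions would not help, because it would still contain nobody with known fish allergy.

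**Working it through.** **Step 1. The plan's own figure.** Section 14 gives n=20 from a 99% confidence level and a confidence interval of 1.35, with no unit, standard deviation or expected rate. For a mean, n = (z × SD / h)², with z = 2.576 for two-sided 99%. Then n=20 requires SD = 1.35 × √20 / 2.576 = 2.34 if 1.35 is the half-width, or 1.17 if it is the full width. If 1.35 is instead a half-width in percentage points for a proportion, n = z² p(1−p)/h² gives 361 at p = 1%. Because an input is missing, n=20 can be neither reproduced nor refuted. It is taken below as the planned minimum of completers, with 30 as the enrolled number.

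**Step 2. Population against claim.**

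| Element | Where | Content |
|---|---|---|
| Allergen source | Section 4 | Fish-derived collagen, plus alginate, CMC, EDTA |
| What is read | Section 8 | Specific IgE already on mast cells |
| Who is left out | Section 5.2 items 3, 8, 12 | Atopic dermatitis or eczema; listed product hypersensitivities; known fish allergy |
| What is concluded | Sections 2 and 14 | Product's sensitization, no population limit |

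The last row is wider than the third row allows.

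**Step 3. Chance of an all-negative table.** Let p be the true positive rate among eligible subjects. The documents give no p, so the values are assumptions. P(0 of n) = (1−p)^n.

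| Assumed p | Expected positives in 20 | P(0 of 20) | P(0 of 30) |
|---|---|---|---|
| 0.5% | 0.1 | 90% | 86% |
| 1% | 0.2 | 82% | 74% |
| 2% | 0.4 | 67% | 55% |
| 5% | 1.0 | 36% | 21% |

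For example, 0.99^20 = 0.818 and 0.95^20 = 0.358. This formula has no term for the exclusion. It shows what a panel of 20 or 30 can and cannot see.

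**Step 4. What a zero count would support.** The exact one-sided 95% upper bound for 0/n is 1 − 0.05^(1/n). For n=20 it is 13.9%, and for n=30 it is 9.5%. Both bounds apply only to people who pass Section 5.2.

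**Step 5. What the exclusion could add.** Suppose a share π of otherwise eligible people is sensitized, a fraction f of them know it and are excluded, everyone sensitized reacts, and there is no other source of positives. The residual rate is r = π(1−f)/(1−πf), and P(at least one positive in 20) = 1 − (1−r)^20.

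| Assumed π | f = 0 | f = 50% | f = 90% |
|---|---|---|---|
| 1% | 18% | 10% | 2% |
| 2% | 33% | 18% | 4% |
| 5% | 64% | 41% | 10% |

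For π = 2% and f = 90%: r = 0.002/0.982 = 0.00204, and 1 − (1 − 0.00204)^20 = 4%. The direction is clear. The size depends entirely on π and f, and the documents give neither.

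**The case against.** A reader might infer that the exclusions build in a near-zero positive count. The documents do not support that. Item 12 removes only known, self-reported fish allergy. Unrecognised sensitization, a reaction to another ingredient and a non-specific wheal all remain possible. No rate is given, and at assumed rates of 1-2% zero is already the most likely count in 20 with nobody excluded. Step 3 therefore mainly reflects the small panel.

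A reader might also take items 3 and 8 as removing everyone previously sensitive to this product, or everyone atopic. Item 8 names product classes and mentions neither this dressing nor collagen. Item 3 covers skin allergy and does not name hay fever, asthma or other food allergy.

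It can further be said that the reference to human subjects in Section 2 tells where the prick is applied, and that Section 14 does not use the phrase. That is fair: the fault is the absence of a limit, not an express claim about all people. Nor does any passage script a finding of no sensitization potential. Section 14 promises a table per subject and a rule built on positive scores. The exclusion is openly listed in Section 5.2 and Appendix I, so it is not hidden.

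Finally, the documents do not say that fish-allergic people react to fish collagen. That also stands, but it supports the limit: the study will have no data on the question in either direction.

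What the objection leaves intact is narrow. The conclusion is framed at product level, the panel excludes known fish allergy, and describing the subjects as healthy does not tell a reader of the report that this group was untested.

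**Conclusion.** The point holds as a correction to the scope of the conclusion. It is not a finding that the wrong people are tested, and it does not make the design invalid. That a negative table cannot inform about known fish-allergic users follows from Sections 4, 5.2 and 8 without any assumed rate.

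The numerical part is secondary. The loss of positives caused by the exclusion cannot be quantified from the documents, and Step 5 is illustration only. The limit set by the panel size can be stated, given independent subjects and 20 completers. Zero positives has probability 82% at an assumed 1% and 36% at an assumed 5%, and an observed 0/20 is compatible with a true rate of up to 13.9% in the screened population.

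**What to change.** 1. Section 2: restate the objective as the wheal response to the test product in healthy adults who meet Sections 5.1 and 5.2, in particular without known fish allergy.
2. Section 14: put the same limit on the product reporting rule. Report the number of positives over the number evaluated at each reading, with an exact confidence interval. The same section says that no statistical analysis will be performed, so the rule's reference to statistical significance has no test behind it and should be reconciled in the same edit.
3. Final report: state that no conclusion is drawn for fish-allergic users.

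The exclusions, procedures and readings stay as they are. The cost is a few sentences and one simple interval per time point. The real downside is a narrower product claim.
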